### **3.5. Assessment of individual service user health and wellbeing outcomes**

The two services collect a range of data about service user outcomes. For the weight management programme service users complete routine service assessments at baseline12 and 26 weeks. For the pulmonary rehabilitation programme assessments are carried out at baseline and on completion of the programme at six weeks. That is after attendance at 8-12 sessions. This is so change can be measured over time.

The researcher will seek consent to access this data for all those service users who attend either of the two participating programmes during the intervention period.

This data will be available at individual service user level if service users give informed consent. This data is stored on the services databases. Only anonymised data will be shared with the researcher.

Additional anonymised demographic data of attendees, that is routinely collected by the services, will be shared with the researcher. This data will include gender, ethnicity, age and index of multiple deprivation.

Primary and secondary outcomes for each of the two participating services will be collected. The outcomes are:

#### Primary outcomes

- LLBD Weight Management Programme: Weight in kilograms
- Pulmonary Rehabilitation Programme: The Chronic Respiratory Disease Questionnaire (CRDQ).

#### Secondary outcomes

- LLBD Weight Management Programme: The short form Warwick and Edinburgh Mental Health and Wellbeing Scale
- Pulmonary Rehabilitation Programme: Incremental shuttle walking test (in meters), Lung Information Needs Questionnaire (LINQ), Generalised Anxiety Disorder Assessment (GAD -7), Patient Health Questionnaire 9 (PHQ-9) and strength tests.

The weight management programme collects service users' weight at 0, 12 and 26 weeks. They collect the short form Warwick and Edinburgh Mental Health and Wellbeing Scale at 0 and 12 weeks.

The pulmonary rehabilitation service collects all measures at 0 and 6 weeks.

We will collect data at baseline and at the end of the programme for both services.

That is:

- 0, 12 and 26 weeks (weight only) for the weight management programme.
- 0 and 6 weeks for the pulmonary rehabilitation programme.

### **3.6. Assessment of service users' subjective Health Literacy skills and health activation**

Services users will be asked to complete an additional questionnaire as part of the research. This will be two domains of the validated Health Literacy Questionnaire (Osborne *et al*; 2013). This is to understand whether their subjective Health Literacy and health activation skills have changed after attending the programmes by Verbal Health Literacy trained or non-trained staff.

The questionnaires will be completed at the same time as the routinely collected service data, that is the secondary outcomes for each service, at baseline, 6 weeks (pulmonary rehabilitation service) and 12 weeks (weight management service).

Service users will complete the questionnaire either electronically or in paper form as per the services current data collection practice. Or they will be posted to participants for them to complete and return. The mode of delivery will depend on the service's preference in order to minimise any extra burden on service staff during the research period.

Consent will be gained from all service user participants prior to collecting their data.

### **3.7. Assessment of changes in outcomes (at a service level)**

Aggregate programme level data will be obtained from the two services for a three - six month period in 2024 when trained staff have delivered programmes and a corresponding three- six month period in 2023. This will allow comparable measurement of change over time at a service level.

For the weight management service, a control group will consist of programmes run by non-trained staff. The same aggregated data will be obtained for this control group. Individual level patient data will not be shared with researchers because not all service users will have consented to this.

The aggregate data will include:

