#### 1.3.6 The services where the intervention will be used

The intervention will be used in two very different services.

1. Live Life Better Derbyshire tier 2 weight management services (Public Health, Derbyshire County Council). The aim of the programme is to help people lose weight. The service provides online and face to face group education and advice programmes that run for one session a week over a rolling 12 week period. The programmes have an accompanying website and resources. The

programme is available for all people in Derbyshire. Eight Public Health Improvement Advisors (HIA's) offer advice to groups of up to 25 people who need to lose weight. 33 programmes run across Derbyshire, 19 online and 14 face to face. Attenders are followed up at 12, 26 and 52 weeks and a weight maintenance programme is available.

2. Derbyshire Community Health Service Pulmonary Rehabilitation programme provided within the NHS. The aim of the programme is to improve people's exercise tolerance and respiratory health. This service provides a six week rolling face to face programme that runs across 6 venues in Derbyshire. 15 members of staff, a mixture of physiotherapists, healthcare assistants and specialist nurses, offer supervised exercise and education and advice to people who are limited by their respiratory condition in Derbyshire. The physiotherapists and specialist nurses lead the sessions and have most contact with patients. Up to 12 people attend two sessions a week over the six week period which are a combination of exercise and education.

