### LLBD weight management programme

- Mean weight and standard deviation at baseline, 12 weeks and 26 weeks
- Mean weight loss and standard deviation between baseline and 12 weeks, and between baseline and 26 weeks.
- Mean score on the short form Warwick and Edinburgh Mental Health and Wellbeing Scale and standard deviation at baseline and 12 weeks.
- Mean change in the short form Warwick and Edinburgh Mental Health and Wellbeing Scale and standard deviation between baseline and 12 weeks s.

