### **3.8 Recruitment**

We will recruit staff delivering Verbal Health Literacy training during a three month period in 2024.

IRAS 336469

V2.0 13052024

We will recruit service users from two services, one within Derbyshire Community Health Services NHS Trust and one within the Local Authority. Service user recruitment is likely to take place over a six month period to recruit the minimum required sample. This is because both services run on a rolling basis. That is week 1 for one person could be week 6 for another.

We will recruit service users who enrol on the 12 week weight management programme and 6 week pulmonary rehabilitation programme after staff have (or have not) attended the Verbal Health Literacy training.

That is:

- Public Health Intervention Advisors and service users from the Live Life Better Derbyshire tier two weight management service.
- Physiotherapists, specialist nurses and service users from the Derbyshire Community Health Services (DCHS) pulmonary rehabilitation service.

Recruitment will commence once HRA and NHS ethics approval is obtained. Written informed consent will be gained for all participants in the study.

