## DCHS NHS Pulmonary Rehabilitation Programme

We would expect the increase in the mean CRDQ score at 6 weeks in 2024 (post training) to be larger than the increase in the mean CRDQ score in 2023 (pre training). We are unlikely to have statistical power to detect small differences based on numbers of service users if we limit the 'post' time period to the three month study period in 2024 and the corresponding 'pre' time period in 2023. We need to extend this request for data to cover a six month period.

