#### 3.10.5 Aggregate service data

For the aggregated outcome data we will compare mean change in an outcome in a three month period before the training and in the three month period after the training for trained and untrained groups. Means and standard deviations will be provided by the services, that is, no individual data will be shared with researchers.

To meet the final objective, we will compare the IMD quintiles for attendees at the programmes in the three month period post-training with the IMD quintiles for the IRAS 336469

Derbyshire population. The expectation is that the % of people in socially deprived quintiles will be higher for the programmes than for the Derbyshire population.

SPSS and Excel spreadsheets will be used to store, organise and assist in analysis of the quantitative data from multiple sources.

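### The service-level cohorts are defined by calendar period alone: no entry rule is given for rolling programmes, and window length and comparison period differ between sections

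*Combined protocol and SAP*

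**What the plan says.** **Period.** Section 3.7 defines the 2024 aggregate data as a "three - six month period in 2024 when trained staff have delivered programmes", set against "a corresponding three- six month period in 2023". Section 3.10.5 says mean changes will be compared "in a three month period before the training and in the three month period after the training". For pulmonary rehabilitation, Section 3.9.3 finds three months too short: "We need to extend this request for data to cover a six month period".

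**Rolling entry.** Weight management offers "one session a week over a rolling 12 week period". For pulmonary rehabilitation, "This service provides a six week rolling face to face programme". Section 3.8 spells out the consequence: "That is week 1 for one person could be week 6 for another".

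**Entry rule.** Section 3.8 limits recruited service users to those who enrol after staff have, or have not, been trained. Sections 3.7 and 3.10.5 contain no such rule for the aggregate data.

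**Outcomes and use.** The aggregate weight outcomes are changes "between baseline and 12 weeks, and between baseline and 26 weeks"; the pulmonary outcomes are at six weeks. Section 3.9.3 attaches the 252-per-group sample size to the service-level weight comparison. Researchers receive only means and standard deviations (Section 3.10.5). Section 6 places training in July to August 2024.

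**The concern.** In a rolling programme a calendar window does not identify a cohort. On the day training is delivered, some people are at week 1 and others are nearly finished. Filtering the extract by outcome date puts people who began before training into the post-training group. Filtering by start date, with a before window that ends at training, lets people in the before group receive part of their programme from trained staff. Either way the before-after contrast moves towards zero.

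The services make this choice when they run the extract, and the researchers cannot undo it because they never hold individual records. A null service-level result could then reflect the filter and not the training.

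**Working it through.** **The plan's own figure.** Inputs from Section 3.9.3: difference 4.7 − 4.3 = 0.4 kg, SD 1.6, 80% power, 5% significance (two-sided assumed, as sidedness is not stated).

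- n = 2 × (1.960 + 0.842)² × 1.6² / 0.4² = 251.2, so 252 per group. The plan's figure is reproduced; power at 252 is 80.1%.

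**Assumptions, none of them given in the documents.** People start at a steady rate; benefit is proportional to the share of the programme delivered after training; three and six months are 13 and 26 weeks. L is programme length, W is window length, and both windows abut the training date.

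**Counting by outcome date.** An outcome recorded t weeks after training, with t uniform on (0, W), has exposure min(t, L)/L. For W ≥ L:

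- share who began before training = L/W
- mean exposure = (L/2 + W − L)/W

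| Outcome | W | Began before training | Mean exposure |
|---|---|---|---|
| 12-week weight | 13 | 12/13 = 92% | 7/13 = 54% |
| 12-week weight | 26 | 12/26 = 46% | 20/26 = 77% |
| 6-week pulmonary | 13 | 6/13 = 46% | 10/13 = 77% |
| 6-week pulmonary | 26 | 6/26 = 23% | 23/26 = 88% |

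For 26-week weight, everyone counted began before training with either window. Mean exposure is 0% (W = 13) or 6/26 = 23% (W = 26).

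**Counting by start date, before window of 13 weeks ending at training.** The post group is fully exposed. In the before group, 12/13 = 92% of weight-management starters finish after training, with mean exposure (12/2)/13 = 6/13 = 46%.

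**Before-after contrast for 12-week weight, 13-week windows.**

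- By outcome date: 7/13 − 0 = 54% of full.
- By start date: 1 − 6/13 = 7/13 = 54% of full.

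The same arithmetic gives 10/13 = 77% for pulmonary rehabilitation.

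**Trained versus untrained difference (the powered contrast).** Standard error at 252 per group = 1.6 × √(2/252) = 0.1425 kg. Power = Φ(difference/0.1425 − 1.960).

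| Rule | Difference | Power at 252 | n per group for 80% |
|---|---|---|---|
| Start date | 0.400 kg | 80.1% | 252 |
| Outcome date, W = 13 | 0.4 × 7/13 = 0.215 kg | 32.7% | 867 |
| Outcome date, W = 26 | 0.4 × 20/26 = 0.308 kg | 57.9% | 425 |

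At the 330 per group mentioned in Section 3.9.3, the three powers are 89.5%, 40.9% and 69.5%.

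**Sensitivity under the outcome-date rule.**

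- If people who began before training gain nothing, the difference is 0.4 × 1/13 = 0.031 kg (power about 4% in the expected direction) with W = 13, and 0.4 × 14/26 = 0.215 kg (33%) with W = 26.
- If a 13-week window opens 4 or 8 weeks after training, the share who began before it falls to 8/13 = 62% or 4/13 = 31%.

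**Window against timetable.** A six-month period lying within 2024 must open by 1 July. It therefore overlaps the July to August training unless all training is complete at the very start of July.

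**The case against.** The strongest case against is that the plan already intends a start-date cohort. Section 3.2 speaks of outcomes for people joining a programme run by trained staff. The 330 per group in Section 3.9.3 is half of the roughly 660 attendees that Section 3.9.2 estimates from numbers joining. Section 3.9.3 also calls the January to March 2023 data a cohort, and labels 2023 the pre-training period. On that reading, Sections 3.7, 3.9.3 and 3.10.5 all mean 2023 against 2024, nobody in the before group is exposed, and nothing is diluted.

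This is a fair reading and may well be the intended one. It is not stated for this extract, and it does not settle three months against six.

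A reader might infer stronger claims, which the documents do not support:

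- *Most people in the post-training data began before training.* No section counts by outcome date. Even under that rule, this is not so for pulmonary rehabilitation (46% or 23%) or for 12-week weight over six months (46%).
- *The post group and the before group are both contaminated.* The two problems need opposite counting rules, so one rule applied to both periods produces only one of them.
- *Exposure in the before group undermines the 252.* That calculation compares trained with untrained groups at 12 weeks, and the before group does not enter it.
- *The individual-level results are diluted too.* The enrolment rule in Section 3.8 protects them.

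**Conclusion.** The point holds as an undefined cohort with inconsistent windows, not as a demonstrated dilution. Sections 3.7 and 3.10.5 give no entry rule; Sections 3.7, 3.9.3 and 3.10.5 disagree on window length and, read literally, on the comparison period.

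It is more than missing detail for two reasons. The literal wording of Section 3.10.5, with windows abutting training, reduces the 12-week before-after contrast to about 54% whichever rule is used. The loss of power from 80% to about 33% or 58% is conditional: it needs outcome-date counting and a window that opens at training. And whichever choice the services make is fixed in the means and SDs they supply.

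The percentages rest on steady intake; the diluted effects and powers rest also on benefit proportional to exposure. A start-date cohort with a 2023 comparator removes the problem. The point should be dealt with before the extract is requested.

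**What to change.** Put the same definition in Sections 3.7 and 3.10.5:

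- **Post cohort:** people whose first session falls after one common date by which training is complete. Use the same date for trained and untrained advisers. Follow each person to their own 6-week, or 12- and 26-week, measure.
- **Comparison cohort:** people whose first session fell in the same calendar months of 2023, followed in the same way.
- **Window:** one stated length per service, consistent with the six months that Section 3.9.3 asks for in pulmonary rehabilitation.

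The direct cost is a few sentences and a date filter in the services' extract. The real cost is time, because the extract must wait for the last starter's outcome. Section 6 gives no separate date for the aggregate extract; its outcome collection ends in February 2025 and analysis in March 2025. Taking training as complete by the end of August:

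- Weight management starters from September to November 2024 reach 12 weeks by 22 February 2025, which fits.
- Their 26-week weights fall between 2 March and 31 May 2025, which does not. Either extend the timetable or limit the 26-week aggregate.
- Six months of pulmonary starters from September run to the end of February 2025, with the last six-week outcome about 11 April 2025. Section 3.7's restriction to 2024 and the timetable both need reconciling with this.

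A 2023 comparator also carries the service improvements that Section 3.9.3 expects between the two years. The untrained groups help with this in weight management, but pulmonary rehabilitation has no such control, and the report should say so.

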### For both services

- Attendance numbers
- Did Not Attend (DNA) numbers and programme completion rates.
- Summarised demographic data of attendees to include numbers and % by gender, ethnicity, age group and index of multiple deprivation quintile.

### LLBD weight management programme

- Mean weight and standard deviation at baseline, 12 weeks and 26 weeks
- Mean weight loss and standard deviation between baseline and 12 weeks, and between baseline and 26 weeks.
- Mean score on the short form Warwick and Edinburgh Mental Health and Wellbeing Scale and standard deviation at baseline and 12 weeks.
- Mean change in the short form Warwick and Edinburgh Mental Health and Wellbeing Scale and standard deviation between baseline and 12 weeks s.

### Pulmonary rehabilitation programme

- Mean CRDQ score and standard deviation at baseline and six weeks.
- Mean change in CRDQ score between baseline and six weeks.
- Mean score in incremental shuttle walking test, LINQ, GAD-7, PHQ-9 and strength test and standard deviation at baseline and six weeks.
- Mean change in incremental shuttle walking test, LINQ, GAD-7, PHQ-9 and strength test between baseline and six weeks.
- Mean change % of service users with Acute respiratory/COPD exacerbation between the same period in 2023 and 2024 (if data available).
- Mean change in % hospital attendance or admission between the same period in 2023 and 2024 (if data available).

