### **3.8.1 Inclusion and exclusion criteria**

Inclusion criteria:

- Public Health Intervention Advisors delivering the tier 2 weight management programme across Derbyshire.
- Physiotherapists and specialist nurses involved in the assessment of patients and delivery of the six week DCHS NHS pulmonary rehabilitation programme.
- Adults aged 18 or over who start the rolling 12 week tier two weight management programme during the intervention period.
- Adults aged 18 or over, with Chronic Obstructive Pulmonary Disease, who are being assessed for and undertaking the six week pulmonary rehabilitation programme during the study intervention period.

- For the staff questionnaire only - Healthcare staff from other services that attend Verbal Health Literacy training, during the study period in 2024, will also be eligible.

Exclusion criteria:

- Service users attending the two service programmes outside of the data collection period.
- Other pulmonary rehabilitation staff. i.e. staff who are not physiotherapists or specialist nurses.

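### The aggregate pulmonary rehabilitation request has no diagnosis breakdown, so the uncontrolled 2023 v 2024 CRDQ comparison could absorb a change in COPD share without the researchers being able to see it

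*Combined protocol and SAP*

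**What the plan says.** **Who is recruited.** Section 3.8.1 of the combined protocol and SAP admits "Adults aged 18 or over, with Chronic Obstructive Pulmonary Disease, who are being assessed for and undertaking the six week pulmonary rehabilitation programme" during the intervention period.

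**Whom the service treats.** Section 1.3.6 describes the programme as being for "people who are limited by their respiratory condition in Derbyshire", which is wider than COPD.

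**What is requested at service level.** Section 3.7 states: "Aggregate programme level data will be obtained from the two services for a three - six month period in 2024", with a corresponding period in 2023. The case-mix items are "Summarised demographic data of attendees to include numbers and % by gender, ethnicity, age group and index of multiple deprivation quintile"; diagnosis is not among them. The CRDQ items are the mean and SD at baseline and six weeks, and "Mean change in CRDQ score between baseline and six weeks". No SD is listed for that change, although one is listed for the weight programme's changes. The exacerbation item, "Mean change % of service users with Acute respiratory/COPD exacerbation between the same period in 2023 and 2024 (if data available"), is also worded more widely than COPD.

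**In what form.** Section 3.7 says "Individual level patient data will not be shared with researchers because not all service users will have consented to this", so the summaries reach beyond the recruited sample. Section 3.10.5 adds: "Means and standard deviations will be provided by the services, that is, no individual data will be shared with researchers".

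**How it is used.** CRDQ is the primary outcome for this service (3.5). Section 3.9.3 expects the 2024 gain in mean CRDQ to exceed the 2023 gain. Section 3.2 explains that a trained v untrained split is not possible in this service. The individual-level analysis in 3.10.4 is a single-group change from baseline to six weeks.

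**The concern.** The year-on-year service-level comparison is the only pulmonary rehabilitation contrast with an untrained period. It has no concurrent control, and no case-mix adjustment or stratification is planned for it.

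Diagnosis is an obvious case-mix variable here, because the protocol itself restricts recruitment on it while describing a wider service. If the proportion of attendees with COPD moved between the 2023 and 2024 windows, and people with COPD gain more or less on the CRDQ than others, the overall mean change would move without any effect of training. With only overall means and SDs, the researchers could neither detect this nor remove it.

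A second consequence is descriptive. The individual-level CRDQ result would concern people with COPD, and the service-level result would concern whoever attended. The protocol does not point this out.

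**Working it through.** **The plan's own figure.** The documents contain no sample size calculation for CRDQ. The one calculation they give, for 12-week weight loss in 3.9.3, confirms the formula used below. With a difference of 4.7 − 4.3 = 0.4 kg, SD 1.6, two-sided 5% and 80% power:

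n = 2 × (1.960 + 0.842)² × 1.6² / 0.4² = 251.2, which rounds up to 252 per group, as stated.

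**Form of the bias.** Let p be the COPD share in a period, and let m_C and m_O be the mean CRDQ gains in users with COPD and other users. Suppose training has no effect, so the gains are the same in both years. The overall mean gain in a period is p × m_C + (1 − p) × m_O. The 2024 minus 2023 difference is then

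bias = (p_2024 − p_2023) × (m_C − m_O).

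It is zero if either factor is zero, and its sign depends on both.

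**Inputs.** The documents give no COPD share, no change in share and no CRDQ gain by diagnosis. Assumed ranges: a shift of 5 to 30 percentage points, and a gap of 0.2 to 0.5 SD of CRDQ change.

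- Low end: 0.05 × 0.2 = 0.01 SD
- Middle: 0.10 × 0.5 = 0.05 SD
- High end: 0.30 × 0.5 = 0.15 SD

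**Scale.** Section 3.9.2 gives 96 to 144 joiners in three months (2 cohorts × 6 venues × 8 to 12 people). Doubling for six months gives 192 to 288. The same number is assumed in 2023, with no drop-out. The difference detectable with 80% power at two-sided 5% is (1.960 + 0.842) × √(2/n). The plan names no test for this comparison. If a two-sided 5% z test were used, the chance of a significant result with no training effect would be Φ(b/se − 1.96) + Φ(−b/se − 1.96), where b is the bias and se = √(2/n).

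| n per period | Detectable difference (SD) | 0.15 SD as a share of it | Rejection rate, bias 0.01 SD | Rejection rate, bias 0.15 SD |
|---|---|---|---|---|
| 96 (three months) | 0.40 | 37% | 5.1% | 18% |
| 144 (three months) | 0.33 | 45% | 5.1% | 25% |
| 192 (six months) | 0.29 | 52% | 5.1% | 31% |
| 288 (six months) | 0.23 | 64% | 5.2% | 44% |

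At the middle value of 0.05 SD, the rejection rate is 7.8% with 192 per period and 9.2% with 288.

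Section 3.9.3 answers low power by extending the request to six months. That reduces random error but leaves this bias unchanged, so the same bias weighs more heavily in the longer window. (Section 3.10.5 still refers to three months.)

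**The case against.** The case on the other side is substantial, and several parts of it stand.

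- **Eligibility.** A reader might infer that attendees without COPD are ineligible and contaminate the service-level data. The documents do not support that. Section 3.8.1 belongs to recruitment. If its exclusions applied to the aggregate data, the one for people attending outside the data collection period would also remove the 2023 comparator. All users of the service are a legitimate service-level population.
- **Whether there is a non-COPD group of any size.** This is inferred from one descriptive phrase in 1.3.6 and the wording of the exacerbation item. Sections 3.8.2 and 3.9.2 invite all joiners and apply no discount for COPD, which would fit a programme that is nearly all COPD. That no diagnosis restriction applies is likewise read from the programme-level wording and is not stated outright.
- **Whether bias has occurred.** A reader might infer that a shift in mix is being counted as a training effect. That needs both a change in share and a difference in gain, and the documents establish neither. With the same service in corresponding periods, a stable mix is plausible.
- **Irreversibility.** A reader might infer that the data can never be filtered. Only the summaries sent to the researchers are fixed. The service holds the records and could run a new extract.
- **Comparability.** A COPD row would not by itself let the individual and service-level results be read together. They would still differ in consent selection and in the contrast made.
- **Feasibility.** The routine demographics in 3.5 do not include diagnosis, and no section says that it can be extracted.

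These points limit how strongly the concern can be put. They do not remove the gap: the comparison is uncontrolled, diagnosis is not requested, and its stability cannot be checked from the data as specified.

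**Conclusion.** The concern holds as a conditional risk and a low-cost improvement, not as a demonstrated bias. The request omits a case-mix variable on which the protocol itself restricts recruitment, and the comparison it feeds has no other protection against a change in mix.

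Size and direction are unknown. Under the assumed inputs the bias runs from negligible (0.01 SD, about 3% to 4% of the difference detectable with six months of intake) to material (0.15 SD, about 52% to 64% of it). If nearly all attendees have COPD in both periods, it is close to zero.

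These figures rest on assumed shifts and gaps, equal numbers in the two years and no drop-out. Diagnosis mix is only one of the possible differences between 2023 and 2024. Dealing with it would not make the comparison a controlled one.

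**What to change.** In 3.7, before the data are extracted and where the service holds diagnosis in extractable form, request every pulmonary rehabilitation outcome summary for both periods in two rows: users with COPD and other users. Each row should give the number, mean, SD, mean change and SD of change. Name the SD of change explicitly. Section 3.7 does not list it for this service, and the baseline and six-week SDs do not yield it without the within-person correlation.

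Report the all-user comparison together with the COPD-only comparison and the COPD share in each period. Say in 3.10.5 that the all-user result covers a wider group than the recruited sample. If diagnosis cannot be extracted, state that as a limitation of the year-on-year comparison.

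The cost is one further split in a summary that the service is already producing. The COPD row will be smaller and less precise than the total, in a comparison whose power 3.9.3 already describes as limited. The all-user mean and SD can be rebuilt from the two rows, so nothing is lost. Other year-on-year confounding remains.
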